**FLE-002 (INSTANT) – Final Analysis**

---

**Statistical Analysis Plan**

---

Refer to section 8.0 of the SAP for a description on the specific cohorts for which Part C MLS results and MLS pooled results will be reported.

---

**FLE-002 (INSTANT) – Final Analysis**

**Statistical Analysis Plan**

---

**15 Programming Specifications**

If required, a separate document will provide details necessary to replicate the various data derivations outlined in the SAP.

**FLE-002 (INSTANT) – Final Analysis****Statistical Analysis Plan****Annex A: FLE-002 Sponsor Review of Adverse Events of Special Interest****1. Background and Justification**

- 1.1 FLE-002 (INSTANT) is the first InCarda Phase 2 clinical study to assess the efficacy and safety of flecainide acetate inhalation solution (FlecIH-103), administered via oral inhalation in patients with recent onset, symptomatic atrial fibrillation (AF). The study is composed of 3 parts which was refined over time through successive protocol amendments (Parts A, B, and C). Part A examined different formulations of inhalation solutions and dosages, leading to the selection of the 120 mg estimated total lung dose (eTLD) of FlecIH-103 formulation administered as two 3.5-minute inhalations separated by a 1-minute break (8 minutes total administration time). This treatment regimen was further evaluated in Parts B and C of FLE-002 and was selected for evaluation in Phase 3.
- 1.2 One of the main objectives of the study, and the focus of the final analysis, is to assess the safety of 120 mg FlecIH-103 inhalation for acute cardioversion of AF. To address this objective, Adverse Events (AEs) were collected by the sites and entered in the Case Report Form (CRF), implemented in an Electronic Data Capture (EDC) system. The AEs were initially also entered in the CRO's Safety Database by the safety team as the MedDRA and WHODrug coding feature in the EDC system (Marvin) was not enabled (in Part A).
- 1.3 Several AEs of special interest (AESIs) were defined for FLE-002, which were progressively refined in subsequent protocol amendments. In February 2021, InCarda amended the FLE-002 protocol (v8.0 EU-1; 16 Feb 2021) with the final pre-defined AESI list and associated criteria, which included: 1) AEs related to the inhalation device; 2) Pregnancy, and; 3) AEs known to be related to other well characterized flecainide formulations (i.e., IV and oral). Criteria for these AESIs and serious AESIs are further defined in Section 5.
- 1.4 Because the definition of AESIs changed over time, and the process to collect them varied between the different parts of the study, InCarda will centrally review all AEs and provide a consistent assessment of AESIs per the criteria described in Section 4 below.

**2. Purpose**

- 2.1 This document outlines the steps required to review all AEs reported in patients who received 120 mg FlecIH-103 in Parts A, B and C of the FLE-002 study to determine if they meet the final AESI criteria as defined in the protocol.
- 2.2 This review will generate data that is to be used in the final analysis of the study, as described in the FLE-002 Statistical Analysis Plan (SAP).

## FLE-002 (INSTANT) – Final Analysis

## Statistical Analysis Plan

### 3. Responsibilities

- 3.1 InCarda Data Management will provide the listing of all AEs, organize data entry, and prepare a memorandum that will record the process execution as per section 5.
- 3.2 InCarda Clinical Development will provide resources to review AEs, enter and verify the new assessments.
- 3.3 InCarda Clinical Operations will archive all relevant documentation in the study Trial Master File (TMF).

### 4. Definitions

- 4.1 Adverse Event (AE): Any untoward medical occurrence in a clinical investigation subject administered a pharmaceutical product and which does not necessarily have to have a causal relationship with this treatment.
- 4.2 AE of Special Interest (AESI): Any AE related to the inhalation device, any pregnancy that started while participating to the study, and AEs known to be related to other formulations of flecainide (i.e., IV and oral).
- 4.3 Non-Cardiovascular Adverse Event of Special Interest (Non-CV AESI): A subset of AEs coded in MedDRA within a System Organ Class (SOC) other than “Cardiac disorders” or “Vascular disorders, which includes AEs related to the inhalation device and any pregnancy that started while participating to the study as defined below:
  - Pregnancy: Any female study subject or female partner of a study subject that becomes pregnant while participating in this study
  - AE related to the inhalation device (nebulizer): AE considered directly related to the nebulizer
- 4.4 Serious Non-Cardiovascular Adverse Event of Special Interest: Non-CV AESI is considered serious if it meets the following criteria.
  - Pregnancy: Any female study subject or female partner of a study subject that becomes pregnant while participating in this study
  - AE related to the inhalation device: AE considered directly related to the nebulizer by the Investigator that meets the definition for a SAE
- 4.5 Cardiovascular Adverse Event of Special Interest (CV AESI): A subset of AEs coded in MedDRA within a System Organ Class (SOC) of “Cardiac disorders” or “Vascular disorders, which include AEs known to be related to flecainide as defined below.

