**Adverse Events of Special Interest (AESI)**

Protocol 8.0/EU-1 uses a new definition of AESI, meaning in the data used for the final report, more than one AESI definition is used.

Protocol 8.0/EU-1 additionally introduces a new category: Serious Adverse Events of Special Interest (SAESI), meaning SAESI was not captured for AESIs reported prior to the introduction of Protocol 8.0/EU-1. The secondary safety endpoint (refer to SAP section 6.2.3.) reports on Serious AESI.

In order to be able to report all AESI and SAESI using the Protocol 8.0/EU-1 definitions, additional source data will be provided by the Sponsor (refer to SAP sections 5.6.5 and Annex A). These data will use a slightly adjusted definition than in protocol 8.0/EU-1 definition for AESI and SAESI, refer to SAP section Annex A .

The protocol 8.0/EU-1 definition of AESI and SAESI is as follows:

Four categories of adverse events of special interest (AESI) are defined. The fourth category described is a subcategory of the third type. For the complete definition of these AESI refer to protocol Section 9.1.2 B:

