### **9.2.2.12 Secondary safety endpoint (MLS)**

The secondary safety endpoint, the incidence of treatment emergent serious adverse events of special interest for flecainide (SAESI, refer to section 3.4 SAP for definition) is reported by analyzing AEs that fulfill all of these conditions:

- Events starts between initiation of inhalation of study drug and Visit 2.
- AE is a SAESI according to sponsor provided information (refer to SAP section Annex A).

Results will be reported for the Safety Population, meaning all subjects who started inhalation of study medication.

The MLS statistical report will summarize results as:

- total number of serious AESI and mean number of serious AESI per subject

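### The secondary safety endpoint (serious AESIs for flecainide) cites the protocol definition but counts by Annex A, whose wording also admits pregnancies and device-related SAEs

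*SAP*

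**What the plan says.** Protocol 7.5.2 B and SAP 6.2.3 name the secondary safety endpoint as the incidence of treatment-emergent serious events of (special) interest for flecainide.

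**The definition cited.** SAP 6.2.3 and 9.2.2.12 both refer to SAP 3.4. That section repeats the protocol 9.1.2.4 B list and says of SAESI: "The fourth category described is a subcategory of the third type". The third type is the set of events known from intravenous and oral flecainide. SAP 3.4 also discloses, of the sponsor-supplied data: "These data will use a slightly adjusted definition than in protocol 8.0/EU-1 definition for AESI and SAESI".

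**The rule that counts.** SAP 9.2.2.12 sets two conditions: "Events starts between initiation of inhalation of study drug and Visit 2", and "AE is a SAESI according to sponsor provided information (refer to SAP section Annex A").

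**Annex A.** Section 4.4 begins "Serious Non-Cardiovascular Adverse Event of Special Interest: Non-CV AESI is considered serious if it meets the following criteria" and has two entries: pregnancy, with no further criterion, and "AE considered directly related to the nebulizer by the Investigator that meets the definition for a SAE". Section 4.5 begins "Cardiovascular Adverse Event of Special Interest (CV AESI): A subset of AEs coded in MedDRA within a System Organ Class (SOC) of" and names the cardiac and vascular classes. Section 4.6 lists six serious cardiovascular items, five of which must also meet the 4.5 definition. The general AESI definition in 4.2 starts "Any AE related to the inhalation device, any pregnancy that started while participating to the study" and sets no organ-class condition.

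**What is to be recorded.** SAP 5.6.5 says the sponsor will state for every AE, yes or no, whether it is an AESI and an SAESI under protocol V8.0. Annex A 2.1 likewise says the review applies the protocol's criteria. The Annex A 5.2.2 form and the sponsor field in the 5.6.5 analysis dataset hold one five-way category. SAP section 10 reports a slightly different definition and lists no changed criterion.

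**The concern.** A safety endpoint needs one rule for what counts. Here the cited definition and the counting rule differ in scope. Two teams following the same SAP could produce different counts, and both could claim to have followed it.

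The difference also touches what the endpoint means. A device-related SAE or a pregnancy is not a flecainide-type event, yet the literal rule adds it to the total and to the percentage of subjects. A reader who expects the protocol definition could not tell from the report how far the reported number departs from it, because the departures are not itemised and no protocol-definition classification is specified.

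**Working it through.** No figure in the plan is at issue, so the check sets the texts side by side.

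**1. Item count.** Protocol 9.1.2.4 B has 6 items: hypotension, ventricular tachycardia (VT), bradycardia, sinus pause, flutter with 1:1 conduction, and any unstable arrhythmia needing treatment. Annex A 4.6 has the same 6, and 4.4 adds 2. Total 6 + 2 = 8.

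**2. Do the two added items enter the endpoint?** SAP 9.2.2.12 requires only that the sponsor classified the event as an SAESI and that it started between inhalation and Visit 2. Serious non-cardiovascular AESI is one of the five sponsor categories. Nothing in 9.2.2.12 limits the total to cardiovascular events, so read literally they count. This does not depend on the subcategory sentence in SAP 3.4, because neither pregnancy nor device events appear in the six-item list. Pregnancy is a remote case, since Visit 2 is Day 5 plus or minus 1 day. The device-related SAE is the practical one.

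**3. Do the 4.5 thresholds narrow the cardiovascular items?**
- Flutter: no change. The protocol item already has 200 bpm.
- Sustained VT: effectively none. More than 30 seconds far exceeds 3 beats.
- Bradycardia: an unstable case that misses the 4.5 rate or duration can still enter through the any-arrhythmia item.
- Sinus pause: gains a floor of more than 3 seconds. The any-arrhythmia item again covers unstable cases that need pacing.
- Hypotension: the only potentially material case. It is not an arrhythmia, so nothing recaptures it. Annex A states below 90/60 mmHg for at least 5 minutes on at least 3 readings; the protocol's serious item states none of these. If SAESI is a subcategory of the third type, however, the same thresholds in protocol 9.1.2.3 B may already apply. Both readings are open.

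**4. Organ class.** Annex A 4.5 confines cardiovascular AESIs to two MedDRA organ classes, and 4.3 confines non-cardiovascular AESIs to the others. Protocol 9.1.2.1 B to 9.1.2.4 B have no such condition. Annex A 4.2 and the available text of 4.7 do not state it either (part of the decision tree may be missing from the text we had). Whether it is a gate or a description is unclear.

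**5. Where would the protocol classification be held?** The five categories do answer the yes/no questions in 5.6.5. But Annex A 5.2.1 gives the reviewer only the Annex A section 4 definitions, so the answers are Annex A answers. One field cannot hold both where the definitions differ. The investigator's SAESI flag cannot stand in throughout: SAP 3.4 says SAESI was not captured for AESIs reported before V8.0. V8.0 is dated 16 February 2021 and Part A closed on 5 March 2020, so the 29 Part A subjects treated with 120 mg FlecIH-103 (protocol 1.4) have none.

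**6. Size of one reclassified subject (illustration).** Neither SAESI counts nor the Part C size are given. Part A 29 + planned Part B 25 = 54.
- 1/54 = 1.85% and 2/54 = 3.70%, a shift of 1.85 points.
- Assuming 20 to 60 Part C subjects, N = 74 to 114, and the shift is 1/74 = 1.35 to 1/114 = 0.88 points.

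**The case against.** The best defence is that little is hidden. The adjusted definition is disclosed in SAP 3.4, 5.6.1, 5.6.5, 9.2.2.9 and 10, and both definitions are printed in the same document. SAP 5.6.5 asks whether each SAESI is cardiovascular and 9.2.2.9 plans that classification, so non-cardiovascular SAESIs were foreseen and can be separated. Listings show investigator and sponsor flags. SAEs remain in the treatment-emergent SAE tables whatever their AESI class. A second person verifies the classifications, and the endpoint has no test or confidence interval.

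All of this stands and limits the weight of the point. It does not settle which count is the endpoint, nor supply the classification that 5.6.5 promises.

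Four stronger readings are tempting, and the documents do not support them:
- **Listed events are lost by coding.** The wording makes this possible. The documents do not show which organ class any such finding receives.
- **Brief treated hypotension must fail the three-reading rule because few readings are scheduled early.** Protocol 6.2.1 B and Table 4 schedule vital signs at conversion to sinus rhythm as well as at fixed times, so this fails for subjects who convert in that interval.
- **Most of the pooled cohort lacks an investigator SAESI flag.** The pool includes Part C, whose size is not given, so the share cannot be computed.
- **The definition was shaped by results.** The trial is open-label, SAP V5.0 (July 2022) follows the last Part C medically-led dosing (December 2021), and 9.2.2.9 says the AESI definition was modified during the trial after data examination and FDA interactions. For the Annex A adjustment itself, 5.6.5 gives alignment with FDA-agreed Phase 3 terms as the reason. A results-driven motive is not shown.

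**Conclusion.** The point holds as an inconsistency of definition. SAP 9.2.2.12 cites the six-item list and counts by an eight-item one. As written, the rule admits pregnancies and device-related SAEs to an endpoint named for flecainide. SAP 5.6.5 and Annex A 2.1 promise the protocol definition, while the specified fields carry only Annex A categories. Calling the change slight understates the addition of a whole class.

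The effect on the result is unknown in size and direction. The 0.9 to 1.9 points per subject rests on the assumed denominators above. The cardiovascular items change little apart from hypotension, where the SAP must say which reading it intends. This deserves correction before the final report, but it does not threaten the trial's other safety reporting.

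**What to change.** 1. Add the protocol V8.0 AESI and SAESI yes/no flags promised in SAP 5.6.5 to the Annex A 5.2.2 listing and to the analysis dataset.
2. In SAP 9.2.2.12, report flecainide-related cardiovascular SAESIs separately from pregnancy and device events. State which count forms the endpoint. Give the protocol V8.0 count beside the Annex A count and list the reclassified events.
3. In section 10, itemise each changed criterion, including the VT change from at least 3 beats to more than 3, which affects the AESI tables only.
4. Reconcile SAP 3.4, 5.6.5, 6.2.3 and 9.2.2.12 with Annex A 2.1 and 4.2 to 4.7. State whether organ class is a gate and whether the hypotension thresholds apply to the serious item. Which clinical threshold is right is for the sponsor to decide.

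The cost is an extra column or two in a review that already covers every AE, a split table and text edits. The downside is two counts to explain.

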8.0 EU-1 Page: 66 of 117 Version

9.1.1 B - Adverse event collection and reporting

All AEs occurring after signature of the study IC and until the EOS are recorded in the eCRF according to the definitions and classifications described under Section 17.2.1. All AEs must be recorded and reported, including AEs that occur during the administration of other drugs. Even if the subject has not yet received the study drug, untoward medical occurrences shall be treated as AEs. After the EOS contact, there is no requirement to actively collect AEs, including deaths.

All laboratory results and vital signs are to be evaluated by the Investigator for clinical significance. Isolated abnormal laboratory results or vital signs findings that are not part of a diagnosis and are considered clinically significant shall be reported as AEs. Medical conditions (including laboratory values/vital signs that are out of range) that were diagnosed or known to exist prior to IC are recorded as medical history.

Adverse events may be directly observed, reported spontaneously by the subject, or reported by the subjects after being questioned by study staff. Holter, ECG and Event Recorder reports may also be used as source to identify AEs. Subjects shall be questioned in a general way, without asking about the occurrence of any specific symptoms. The Investigator must assess all AEs to determine seriousness, severity, and causality, in accordance with the definitions in Section 17.2.1. The Investigator's assessment must be clearly documented in the site's source documentation with the Investigator's signature.

All SAEs recorded on the AE eCRF page, that meet seriousness criteria (see Section 17.2.1.2) or that meet the criteria for AESI (serious or non-serious; see Section 9.1.2 B) must be reported within 24 hours of the Investigator's awareness. If all the required information is not available, the information which is available is to be recorded without delay (within 24 hours), and the outstanding data recorded as soon as available thereafter. Responses to queries related to the reported SAE or AESI must be provided as soon as possible.

In case of an occurrence of an AE, the Investigator must ensure appropriate medical treatment and shall decide whether to discontinue or interrupt the study drug, as applicable.

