9.1.2.1 B – AEs related to inhalation device

Events related to the inhalation device (AeroEclipse® II BAN) are considered AESI. All AEs related to inhalation device are followed to conclusion to determine their outcome. Inhalation devices associated with AESIs are to be retained and returned to the Sponsor for further evaluation as appropriate.

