## FLE-002 (INSTANT) – Final Analysis

## Statistical Analysis Plan

### 4.7 Decision Tree

Non-CV AESI = Pregnancy and AEs related to the inhalation device (nebulizer)

CV AESI = Hypotension, ventricular tachycardia, bradycardia, sinus pause post-cardioversion, and atrial flutter with 1:1 conduction with fast ventricular response

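### SAP Annex A 4.3 and 4.5 tie AESI status to MedDRA organ class, which contradicts Annex A 4.2 and 4.7 and the protocol and, read literally, reclassifies two kinds of protocol AESI as Non-AESI

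*SAP*

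**What the plan says.** Annex A of the SAP has the sponsor go through all AEs and place each in one of five types: Non-AESI, or an AESI that is cardiovascular or not and serious or not. Two definitions carry a coding condition. Annex A 4.3 reads "Non-Cardiovascular Adverse Event of Special Interest (Non-CV AESI): A subset of AEs coded in MedDRA within a System Organ Class (SOC) other than" the cardiac and vascular classes, and lists pregnancy and device-related events. Annex A 4.5 reads "4.5 Cardiovascular Adverse Event of Special Interest (CV AESI): A subset of AEs coded in MedDRA within a System Organ Class (SOC) of" cardiac or vascular disorders, and lists five events: hypotension, ventricular tachycardia, bradycardia, sinus pause after conversion, and 1:1 atrial flutter.

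Other parts of the same annex have no such condition. The parent definition in 4.2 covers "Any AE related to the inhalation device, any pregnancy that started while participating to the study", together with events known from other flecainide formulations. The decision-tree text in 4.7 states "CV AESI = Hypotension, ventricular tachycardia, bradycardia, sinus pause post-cardioversion, and atrial flutter with 1:1 conduction with fast ventricular response", and defines the non-cardiovascular group as pregnancy and device-related events. Annex A 2.1 gives the purpose as checking AEs against the protocol's final AESI criteria.

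The protocol criteria are clinical. Section 9.1.2.1 B makes device-related events AESIs whatever their coding and adds "All AEs related to inhalation device are followed to conclusion to determine their outcome". Section 9.1.2.3 B defines the five cardiovascular events by blood pressure, ECG findings and rate.

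SAP 9.2.2.9 tabulates AESIs and serious AESIs from the sponsor's classification, and SAP 9.2.2.12 bases the secondary safety endpoint on it. SAP Section 10 discloses a slightly different AESI definition and refers to Annex A without naming the organ-class condition.

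**The concern.** An AESI definition should turn on what happened to the subject. Here two of the governing definitions also turn on how the reported term was coded, and two others do not. The assessor receives all of Annex A section 4 (5.2.1), works from a listing that shows the organ class (5.1.1), and may pick only one type per event (5.2.2). No rule says which definition prevails, so two careful assessors could place the same event differently.

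At stake are the completeness of the AESI tables and, through them, the secondary safety endpoint. Annex A 4.6 defines the five named serious cardiovascular events by reference to 4.5, so the condition carries into serious hypotension and bradycardia. Annex A 4.4 likewise starts from the non-cardiovascular AESI of 4.3. The study is open-label, and this SAP version (6 July 2022) postdates the last medically-led treatment (7 December 2021, SAP 1.1.1). A sponsor rule written at that stage should leave no such discretion.

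**Working it through.** The plan gives no figure to reproduce. The check is an enumeration of three yes/no attributes: coded in a cardiac or vascular class, meets one of the five criteria in 4.5, and device-related. That gives 2 × 2 × 2 = 8 combinations. Pregnancy is left aside.

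| Cardiac/vascular class | Meets a 4.5 criterion | Device-related | Literal 4.3 and 4.5 | 4.2, 4.7 and protocol |
|---|---|---|---|---|
| yes | yes | yes | CV AESI | AESI (fits both types) |
| yes | yes | no | CV AESI | CV AESI |
| yes | no | yes | **Non-AESI** | Non-CV AESI |
| yes | no | no | Non-AESI | Non-AESI |
| no | yes | yes | Non-CV AESI | AESI (fits both types) |
| no | yes | no | **Non-AESI** | CV AESI |
| no | no | yes | Non-CV AESI | Non-CV AESI |
| no | no | no | Non-AESI | Non-AESI |

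Six combinations hold an AESI under the protocol. The literal text keeps 4 of 6 and loses 2 of 6. Without the organ-class condition, 0 of 6 are lost.

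**Can the lost combinations occur?** The device-related one follows from the text alone: 4.3 excludes the event by class, and 4.5 has no device item. The other requires a qualifying event to be coded outside the two classes. Protocol 9.1.1 B gives a possible route: "Isolated abnormal laboratory results or vital signs findings that are not part of a diagnosis and are considered clinically significant shall be reported as AEs". SAP 5.6.4 records two Part A AEs in the 120 mg FlecIH-103 group that were also coded to a general-disorders class. Their nature is not stated and they kept their original coding, so they show only that coding outside the two classes happens. The documents do not say where a low blood pressure or heart-rate reading would be coded.

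**Serious events.** The any-arrhythmia item in 4.6 may recover unstable rhythm events that needed intervention, but it does not cover hypotension.

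**What one subject is worth (illustration only).** Part A treated 29 subjects with 120 mg FlecIH-103 (protocol 1.4), and Part B planned about 25. The Part C number is not given. 29 + 25 = 54, and 100/54 = 1.85 percentage points per subject. With an assumed 80 subjects it is 100/80 = 1.25 points, and with an assumed 100 it is 1.0 point.

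**The case against.** The strongest reply is that nothing is certain to be lost. Annex A 4.2 and 4.7 keep both kinds of event as AESIs, the assessor has all of section 4, and 2.1 states the protocol criteria as the aim. That stands: the defect is an internal contradiction with a literal reading that loses events. A reader might infer that these events drop out of every AESI category. The text of 4.2 and 4.7 does not support that.

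A reader might also infer that Annex A sorts by organ class first. The text gives no order of steps, and any decision-tree graphic is missing from the available copy, so this cannot be confirmed. Nor are all device-related events coded as cardiac or vascular at risk. One that meets a 4.5 criterion stays a CV AESI.

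The route through isolated vital-sign findings is narrow. A sustained low pressure or rate that meets 9.1.2.3 B is already named hypotension or bradycardia there, and protocol 1.4 describes Part A events in those diagnostic terms. Serious forms need clinical instability and intervention, so few would be reported as isolated findings. This argues for a small effect; it does not make the rule correct.

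There are safeguards: safety-database reconciliation with re-evaluation of coding for Parts B and C (SAP 5.6.3), second-person verification (Annex A 5.3), listings that show investigator or CRO flags beside the sponsor's, and tables of all AEs by class and term. They keep events visible, but they leave the contradictory rule in place, and the AESI tables and the endpoint use the sponsor's result.

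Finally, the SAP says openly that its definition is adjusted, to align with Phase 3 terms (5.6.5). Annex A 4.5 does contain another change from the protocol, a stricter beat count for ventricular tachycardia. The general disclosure therefore does not show that an organ-class condition was intended, and 4.2 and 4.7 suggest that it was not.

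**Conclusion.** The point holds as a contradiction within Annex A, and between Annex A and the protocol, that should be corrected. Read literally, 4.3 and 4.5 turn two of six protocol AESI combinations into Non-AESI, and the condition can reach serious AESIs and the secondary safety endpoint, though probably in few cases.

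The frequency is not in the documents, so no percentage undercount of hypotension or bradycardia can be claimed. A reader might infer a systematic undercount. That would need evidence on how vital-sign terms were coded, which is an assumption the sponsor can check in its coded listing. The part of the finding on device-related events rests on no such assumption. The 1.0 to 1.9 points per subject are illustrative and depend on assumed denominators.

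**What to change.** Delete the organ-class condition from Annex A 4.3 and 4.5. Assign AESI status by event criterion, device relation or pregnancy alone, as 4.2, 4.7 and the protocol do, and use organ class at most as a display label.

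Because 5.2.2 allows only one type per event, add one precedence sentence for events that are device-related and also meet a 4.5 criterion. Allowing two flags would conflict with 5.2.2 and with the five-option variable in SAP 5.6.5. The sentence should also say whether 4.4 or 4.6 governs seriousness for such events, since the two tests differ. Device relation is recorded separately for every AE (SAP 9.2.2.9), so it stays available whichever category takes precedence.

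The cost is two edited definitions and one added sentence. The assessor already reads every AE. If the review has been completed, only events in the two affected combinations, and those that fit both categories, need another look. They can be found by filtering the coded listing on organ class, device relation and reported term.
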